5. TREATMENT OF SUBJECTS

5.1. Investigational product/treatment

Anidulafungin

Detailed information on anidulafungin, the investigational product used in this study can be found in the SPC. A short summary is given here. The information currently available on combination therapy with a triazole and an echinocandin for the treatment of IA is described below (6.2).

Mechanism of action

Anidulafungin is a semi-synthetic echinocandin, a lipopeptide synthesised from a fermentation product of Aspergillus nidulans. Anidulafungin selectively inhibits 1,3-8-D glucan synthase, an enzyme present in fungal, but not mammalian cells. This results in inhibition of the formation of 1,3-beta-D-glucan, an essential component of the fungal cell wall. Anidulafungin has shown fungicidal activity against Candida species and activity against regions of active cell growth of the hyphae of Aspergillus fumigatus.

Chemical Name

Anidulafungin has the chemical name 1-[(4R,5R)-4,5- Dihydroxy-N2- [[4"-(pentyloxy) [1,1':4',1"-terphenyl]- 4- yl]carbonyl]- Lornithine]echinocandin B.

Name of medicinal product

ECALTA 100 mg powder for concentrate for solution for infusion

Method of administration

For intravenous use only.

ECALTA should be reconstituted with water for injections to a concentration of 3.33 mg/mL and subsequently diluted to a concentration of 0.77 mg/mL.

Dosage & duration

Adult patients receive a loading dose on day-1 of 200mg IV, followed by 100 mg daily thereafter.

Anidulafungin will be given for at least 7 days but no longer than 28 days. Please note that this refers to the MITT primary endpoint population. In patients in which triazole resistance is demonstrated or in which the results of the resistance test are inconclusive, the treatment duration of combination therapy can be much longer. These patients are not included in the MITT primary endpoint population.

Intervention

Treatment with a triazole (voriconazole or isavuconazole or posaconazole) + anidulafungin IV. The triazole is administered for at least 6 weeks while anidulafungin is given for at least 7 and a maximum of 28 days.

Comparator

Treatment with a triazole (voriconazole or isavuconazole or posaconazole) for at least 6 weeks.

In both groups, the route of administration is according to the choice of the treating physician as well as the decision to perform or not perform therapeutic drug monitoring of the triazole drug.

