7.1.2. Secondary study endpoints

- 1. Overall aspergillus attributable mortality 12 weeks after the start of antifungal therapy(*).
- 2. Overall survival 12 weeks after the start of antifungal therapy in the MITT population
- 3. Overall survival 6 weeks after the start of therapy in the subgroup of patients in the MITT population with a positive serum galactomannan test at baseline.
- 4. Overall survival 6 weeks after the start of therapy in the subgroup of non-ICU patients who fulfill the EORTC/MSG probable or proven definition (MITT population).
- 5. Overall survival 6 weeks after the start of therapy in the subgroup of non-ICU patients with an underlying haematological disease (MITT population)
- 6. Overall survival 6 weeks after the start of therapy in the subgroup of non-ICU patients without an underlying haematological disease (MITT population)
- 7. Overall survival 6 weeks after the start of therapy in patients that started with triazole monotherapy and in which triazole resistance is detected during follow-up (MITT population)
- 8. Overall survival 6 weeks after the start of therapy in patients that started with triazole-anidulafungin combination therapy and in which triazole resistance is detected during follow-up (MITT population)
- 9. In the subgroup of patients with a positive serum galactomannan; Kinetics of serum galactomannan levels with combination versus monotherapy
- 10. Outcome of patients in which resistance testing was unsuccessful
- 11. Time to hospital discharge (in the MITT subgroup of patients admitted to the hospital at baseline)
- 12. Cost-effectivity of azole-anidulafungin combination therapy
- (*) Aspergillus attributable mortality is defined according to Vidal G et al. (with some modifications) as one of the following²²:

When selecting one of the 4 options below, please consider the immediate cause of death as the disease process, injury, or complication immediately preceding death.

IA is considered the cause of death (=IA attributable mortality)

1. IA was considered the cause of death when the immediate cause of death was due to this infection. Examples are neurological complications of an aspergillus infection

- that disseminated to the brain, lung bleeding or respiratory insufficiency in a patient with pulmonary aspergillosis *or*

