7.1.4. Definitions of the patient populations

ITT: All patients randomized as registered in the IVRS

MITT: All patients randomized as registered in the IVRS, in whom the positive mycological test was available at the time of randomization or became available within 8 days after randomization will be included in the MITT population unless resistance to voriconazole was documented by culture or PCR (VIPcheck or Aspergenius, see below). Because Dutch guidelines currently recommend initiating combination antifungal therapy if the presence of an azole resistant A. fumigatus infection cannot be excluded by PCR or culture, Dutch patients in whom the resistance PCR or culture turns out unsuccessful will be excluded from the MITT population as well. The antifungal therapy given to these patients will be decided upon by their treating physician (see also flowdiagram).

ICU population: Patients already admitted to the ICU at the time of the start of triazole antifungal therapy

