9.2. Secondary endpoints analyses

The 1st secondary endpoint is defined as attributable mortality at 84 days (12 weeks) follow-up, which will be analyzed in the main analysis population. For this analysis, non-attributable mortality will be considered competing risk for attributable mortality For the analysis of secondary endpoints 2 to 6 see 9.1.

Secondary endpoints 7 and 8 will be analysis using descriptive statistics (6- and 12-week mortality with 95% confidence intervals). If the number of patients in the 2 subgroups described in endpoint 6 and 7 are sufficiently large (\square 25) we will compare the 6 mortality of both groups using the Fisher-Exact test.

Regarding endpoint 9, several studies have studied the impact of galactomannan kinetics on outcome in patients with IA. Studies have shown a reasonable correlation between galactomannan kinetics in the weeks following the initiation of therapy and outcome²¹. However, several questions remain; What is the optimal timing of the follow-up galactomannan measurement? Is the rate of decline more informative than a simpler binary outcome (decline/no decline or decline with 0.5 OD units)? The statistical analysis plan for this endpoint will be written when the study is completed, and the number of galactomannan positive patients and the number of follow-up plasma samples is known.

Secondary endpoints 10 will be analysis using descriptive statistics (6 and 12-week mortality with 95% confidence intervals).

The 11th secondary endpoint is defined as the total duration of the hospital stay. The relation between randomly allocated treatment and this secondary endpoint will be analyzed using a Mann-Whitney U test.

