- **5.** Inherited severe immunodeficiency (eg, chronic granulomatous disease, severe combined immunodeficiency).

Clinical criteria

Must be consistent with the microbiological findings, if any, and must be temporally related to current episode. Every reasonable attempt should be made to exclude an alternative etiology.

1. Lower respiratory tract fungal disease

The presence of one of the following three signs on CT:

- · Dense, well-circumscribed lesion with or without a halo sign;
- · Air crescent sign;
- · Cavity.
- For patients with a serum galactomannan value of 0.5 or higher or for patients with a BAL galactomannan of 1.0 or higher, the presence of any pulmonary infiltrate is considered sufficient evidence of lower respiratory tract fungal disease

2. Tracheobronchitis:

Tracheobronchial ulceration, nodule, pseudomembrane, plaque or eschar seen on bronchoscopy.

3. Sinonasal infection

Imaging showing sinusitis PLUS at least one of the following:

- Acute localized pain (including pain radiating to the eye);
- Nasal ulcer with black eschar;
- · Extension from the paranasal sinus across bony barriers, including into the orbit.

4. CNS infection

At least one of the following:

- · Focal lesions on imaging;
- Meningeal enhancement on MRI or CT.

MYCOLOGICAL CRITERIA

- 1. Cytology, direct microscopy or culture:
- · Sputum, BAL and bronchial brush samples demonstrating the presence of fungal elements either by recovery by culture of Aspergillus spp. or detection by cytology or
- · direct microscopy of hyphal forms in combination with a positive aspergillus PCR on sputum, BAL or bronchial brush
- · Sinus aspirate: recovery by culture of Aspergillus spp. from aspirate or the detection of hyphal forms by cytology or microscopy in combination with a positive aspergillus PCR on the aspirate.
- · Skin ulcers, draining soft tissue lesions or fissure for which both a positive microscopy (hyphae) and positive Aspergillus culture are required.
- 2. Detection of galactomannan antigen or DNA of aspergillus defined as one of the following:
- Galactomannan antigen EIA (Platelia):
 - 1. Serum sample positive for galactomannan (0.5 or higher);
 - 2. BAL sample positive for galactomannan (1.0 or higher).
- PCR:
 - 1. Positive Aspergenius spp. PCR on BAL fluid (cycle threshold 38 or lower) in combination with a galactomannan BAL OD value of 0.5-0.9 is considered a positive mycological criterium in this study

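### Secondary endpoints 7 and 8 are set in the MITT, which excludes their own patients, and the Fisher test in 9.2 names endpoint 6 in place of 8; endpoint 4's definition is ambiguous

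*Protocol*

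**What the plan says.** **Resistance endpoints.** Protocol 7.1.2 (and the Summary) gives endpoint 7 as 6-week survival in patients who "started with triazole monotherapy and in which triazole resistance is detected during follow-up (MITT population". Endpoint 8 covers those who began "triazole-anidulafungin combination therapy and in which triazole resistance is detected during follow-up (MITT population". Secondary objective 2 (section 2) rests on these two endpoints, and endpoint 8 is the third goal listed in section 1.

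**The MITT.** Section 7.1.4 says that patients with timely positive mycology "will be included in the MITT population unless resistance to voriconazole was documented by culture or PCR", with no time limit on when the resistance is documented. Section 5.1 speaks of patients with demonstrated triazole resistance or an inconclusive test and states: "These patients are not included in the MITT primary endpoint population".

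**The test.** Section 9.2 assigns descriptive statistics to endpoints 7 and 8. The next sentence reads "If the number of patients in the 2 subgroups described in endpoint 6 and 7 are sufficiently large" and goes on to a Fisher exact test of mortality at 6, with the unit missing. The sign before the threshold of 25 is not legible in the text at hand; I read it as at least 25.

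**Endpoint 4.** This is survival in "the subgroup of non-ICU patients who fulfill the EORTC/MSG probable or proven definition (MITT population". In Appendix 1 (clinical criteria, lower respiratory tract), once serum galactomannan is 0.5 or higher or BAL galactomannan is 1.0 or higher, "the presence of any pulmonary infiltrate is considered sufficient evidence of lower respiratory tract fungal disease". Appendix 1 also defines a separate *suspected* category for atypical infiltrates and says that EORTC/MSG has no such category.

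**The concern.** An endpoint restricted to patients with a given feature, within a population defined by the absence of that feature, has nobody in it. An analyst who follows the labels would report nothing for endpoints 7 and 8. Resistant infection by initial therapy is one of the trial's two stated reasons for existing (section 1), and the Fisher test is the only comparison planned for it. Taken literally, that test sets non-ICU patients without haematological disease, both arms together, against monotherapy patients with resistance, a contrast with no meaning.

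Endpoint 4 raises a different problem. Its name points to classical probable or proven disease, but the study's own Appendix 1 widens *probable*. Two analysts could select different patients.

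**Working it through.** **1. The plan's own figure.** Section 9.5 uses 35% against 23.33% mortality and 80% power; 9.3 gives two-sided 0.05. With pooled variance and no continuity correction:

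n = [1.960·√(2 × 0.29165 × 0.70835) + 0.842·√(0.35 × 0.65 + 0.2333 × 0.7667)]² / 0.1167² = (1.260 + 0.537)² / 0.01362 ≈ 237 per group.

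This reproduces the stated 237 (474 in total). Nothing below changes it.

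**2. Endpoints 7 and 8 against the MITT.**

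- Required by the endpoints: triazole resistance detected, and MITT membership.
- Removed from the MITT by 7.1.4: documented voriconazole resistance.
- Overlap under 7.1.4 alone: only isolates resistant to itraconazole or posaconazole but not to voriconazole.
- Overlap once 5.1 is added (demonstrated triazole resistance is outside the MITT): none.

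The set is empty or nearly so. Endpoint 10 also concerns patients partly outside the MITT and carries no MITT label, which suggests that the label on 7 and 8 is a slip.

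**3. The Fisher sentence.** Endpoint 6 contains both arms and is not a resistance group; 9.1 already gives it logistic regression. The preceding sentence names 7 and 8. The reference is off by one.

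**4. How many patients a corrected label would give.** Assume 474 MITT patients, all susceptible, no other exclusions, and prevalence r between 5% and 15% (section 1). Then the number resistant = 474 × r / (1 − r).

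| r | Resistant | Per arm |
|---|---|---|
| 5% | 474 × 0.05 / 0.95 = 24.9 | 12.5 |
| 15% | 474 × 0.15 / 0.85 = 83.6 | 41.8 |

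Section 1 says that about 35% of patients have no interpretable resistance result. Section 7.1.4 removes such patients from the MITT in the Netherlands only. If instead all of them stayed in the MITT (the Belgian rule applied throughout), the number detected = 474 × 0.65r / (1 − 0.65r):

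- r = 5%: 474 × 0.0325 / 0.9675 = 15.9, about 8 per arm.
- r = 15%: 474 × 0.0975 / 0.9025 = 51.2, about 26 per arm.

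Twenty-five per arm means 50 detected. That needs r = 50 / (474 + 50) = 9.5% in the first case and 9.5% / 0.65 = 14.7% in the second.

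**5. Endpoint 4.** Take a non-ICU patient with a host factor and pulmonary disease. Cross typical or atypical CT with galactomannan at or above the cut-off, positive culture, and the PCR-plus-intermediate-galactomannan rule. Ten patterns have positive mycology:

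| Pattern | Count | Inclusion criteria 4-5 | Appendix 1 class |
|---|---|---|---|
| Typical CT | 5 | met | probable |
| Atypical, galactomannan positive | 2 | met | probable and suspected |
| Atypical, galactomannan below cut-off | 3 | not met | suspected only |

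All 7 patterns that meet criteria 4-5 are *probable*, so on that literal reading endpoint 4 is the whole non-ICU MITT. But section 4.1 admits any infiltrate with a positive BAL culture, which covers two of the last three patterns (taking the culture as BAL), and endpoint 4 is then a proper subset. If the unmodified EORTC/MSG radiology is meant, the two overlapping patterns drop out as well.

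**The case against.** The best defence is that the intent is recoverable. Sections 1 and 2 identify the resistance patients plainly, survival is collected after patients go off study (7.6, 12.1), and the sentence before the Fisher test names the right endpoints. Endpoints 7 and 8 are mainly descriptive. All of that stands: no data are lost, and the cross-reference is clerical. It does not rescue the label, because 7.1.4 defines only one MITT and 5.1 repeats the exclusion.

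A reader might infer that endpoint 4 simply is the non-ICU MITT. The documents do not support that as fact. Section 4.1 separates proven and probable cases from atypical infiltrates, Appendix 1 keeps *suspected* apart, and inclusion criterion 7 uses the EORTC/MSG CT criteria in the strict sense. A proper subset was intended. Nor can it be said that endpoint 4 holds twice the intended patients: the 50% with atypical findings in 7.1.3 is an upper figure for real-life practice, and patients entering under criterion 7 must have the strict signs.

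It is also tempting to apply the resistance prevalence to every randomised patient. That overstates the yield, since the endpoints count detected resistance and the randomised set includes patients whose mycology never turns positive.

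**Conclusion.** The population label on endpoints 7 and 8 is wrong as written, and so is the endpoint pair in the Fisher sentence. Followed literally, objective 2 and the third study goal receive no or almost no data. Under a corrected label about 25-84 resistant patients (12-42 per arm) might be expected, or about 16-51 if patients without a test result all remain in the MITT. These counts are illustrative. They rest on the section 1 prevalence range applying to the enrolled patients and on no MITT exclusions beyond those modelled. The formal comparison is uncertain at either end; the descriptive estimates with confidence intervals are what the correction secures.

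For endpoint 4 the finding is narrower: *probable* and *suspected* overlap, and 4.1 does not agree with inclusion criterion 4, so the subgroup is not uniquely defined. The primary endpoint, its alpha and its sample size are untouched.

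**What to change.** - **7.1.2 and Summary, endpoints 7 and 8:** replace the MITT label with all randomised patients with documented triazole resistance, by allocated initial therapy. An acceptable alternative is the MITT with only the resistance exclusion lifted, which keeps the 8-day mycology rule. The sponsor should choose one before outcome data are analysed.
- **9.2:** refer the Fisher test to endpoints 7 and 8, and give the mortality time point as 6 weeks.
- **Endpoint 4:** state that it requires the strict CT signs named in inclusion criterion 7, without Appendix 1's any-infiltrate bullet, and reconcile section 4.1 with inclusion criterion 4. Dropping that bullet alone does not restore the unmodified EORTC/MSG definition, because Appendix 1 has other study-specific changes (for example the PCR rule and the allowance for newly diagnosed AML). The text should not claim that it does.

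The cost is a few wording changes. No new data are needed for endpoints 7 and 8: 7.6 follows withdrawn patients for mortality, and 12.1 keeps survival and antifungal therapy for those going off study.

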7.1.3. Pragmatic study design

We have tried to design the study in such a way that the prompt inclusion of patients is facilitated as much as possible.

- 1. Registration trials of new antifungal drugs typically only include patients that fulfill the strict lung CT radiology criteria (e.g. halo sign) as described in appendix 1. However, in real-life as much as 50% of the patients treated for invasive aspergillosis do not have these typical abnormalities but are treated on the basis of the presence of a host factor, a positive mycological test and a (non-typical) pulmonary infiltrate. The outcome of these patients is similar to those with the typical pulmonary infiltrate. ¹² Therefore, we consider the exclusion of these patients undesirable in the context of a pragmatic trial.
- 2. Typically, patients that have received antifungal therapy for more than 48-96 hours at the time of inclusion are excluded from registration trials. Again, this leads to many patients being excluded from study participation. To avoid this, we will allow that patients at high risk of IA (patents with AML or grade II or higher GVHD) are included at the time the triazole antifungal therapy is initiated by the treating physician even when the mycological criterium is not yet met. These patients will

- be followed until day 7 and will leave the study if at that time the mycological tests have turned out to be negative.
- 3. While the previous randomized study on the use of combination antifungal therapy for IA only included patients with an underlying haematological disease, there is no reason to believe that the hypothesis of improved survival with combination therapy only applies to these patients. Therefore, our study population will not be limited to this subgroup of patients.
- 4. Our study design has overall mortality as the primary endpoint and no compulsory follow-up CT scans are required.
- 5. Given the 100% objective primary endpoint we have decided not to use a doubleblind design. This will make the study logistics and therefore the inclusion of patients more straightforward. By offering state-of-the-art triazole resistance testing to all patients, the presence of triazole resistance is made very unlikely and therefore the treating physician can be reassured that the treatment given to patients in the control arm is a fully active treatment.

7.1.4. Definitions of the patient populations

ITT: All patients randomized as registered in the IVRS

MITT: All patients randomized as registered in the IVRS, in whom the positive mycological test was available at the time of randomization or became available within 8 days after randomization will be included in the MITT population unless resistance to voriconazole was documented by culture or PCR (VIPcheck or Aspergenius, see below). Because Dutch guidelines currently recommend initiating combination antifungal therapy if the presence of an azole resistant A. fumigatus infection cannot be excluded by PCR or culture, Dutch patients in whom the resistance PCR or culture turns out unsuccessful will be excluded from the MITT population as well. The antifungal therapy given to these patients will be decided upon by their treating physician (see also flowdiagram).

ICU population: Patients already admitted to the ICU at the time of the start of triazole antifungal therapy

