Another important reason to study upfront combination therapy for patients with IA in the Netherlands and Belgium is the increasing incidence of triazole-resistant A. fumigatus. Indeed, from a global perspective the highest prevalence of triazole resistance has been documented in the Netherlands. It increased from 0% before the year 2000 to 5.3% in 2009, and further increased to 15% in 2017. Unfortunately, more recently triazole resistance was observed in 5% of IA cases in Belgium as well and in 2017 researchers from the Erasme hospital in Brussels even reported a prevalence of 13% (Vermeulen et al., 2015⁵; Montesinos et al., 2017⁶). It has also clearly been demonstrated that the overall mortality becomes very high (50-88%) when patients infected with a triazoleresistant A. fumigatus initially receive inappropriate voriconazole therapy and therapy is only changed at a time when it has become clinically obvious that the IA is progressing (Lestrade et al., 2018⁷, van der Linden et al., 2015⁸; Chong et al., 2015⁹). These important observations recently led to a change in the treatment recommendations of the 2017 Dutch SWAB guideline on fungal infections. In the absence of any evidence from prospective studies on the treatment of IA in regions with a high prevalence of azole resistance, this guideline recommends 2 possible strategies. The first is upfront combination therapy (triazole combined with an echinocandin or liposomal amphotericin B) until resistance can be excluded. The second option, which should only be considered in non-critically ill patients and in centers that are able to perform real-time PCR as well as cultured based resistance testing on BAL samples, is to start with voriconazole monotherapy while waiting for the resistance test (Kullberg et al., 2018¹⁰). Unfortunately, resistance testing will not lead to an interpretable result in approximately 35% of the patients with IA. Indeed, fungal cultures remain negative in the majority of the patients with IA and PCR testing for CYP51 resistance associated mutations is not always successful either. For this subgroup of patients, the SWAB guideline recommends switching from triazole monotherapy to combination therapy as soon as it becomes clear that no resistance result will become available. The latter recommendation has been criticized when it relates to patients that are not very sick and have an infection that is limited to the lungs and that is not widespread. Indeed, some clinicians argue that close monitoring for treatment progression is a valid option as well because the poor outcome of azole resistant IA has not (yet) been convincingly demonstrated for culture negative cases.

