2. OBJECTIVES

Primary objective

1. Evaluate if the survival in patients with a triazole susceptible IA can be improved when the initial therapy consists of triazole and echinocandin combination therapy instead of triazole monotherapy. This objective is captured in the primary endpoint as well as secondary endpoints 1 to 6)

Secondary objectives

- 1. Evaluate if a triazole/echinocandin combination therapy improves the overall quality of life and if it is a cost-effective intervention (these objectives are captured in secondary endpoint 11 and 12)
- 2. Evaluate the outcome of patients in which a triazole-resistant A. fumigatus is detected in relation to the initial antifungal therapy they had received (i.e. triazole monotherapy or combination therapy). This objective translates into secondary endpoint 7 an 8.
- 3. Evaluate the outcome of patients in which resistance testing is unsuccessful in function of the antifungal therapy they received. This translates into secondary endpoint
- 4. Evaluate if the baseline serum galactomannan value and the serum galactomannan kinetics are predictive of overall 6-week survival. This translates into secondary endpoint 3 and 9.

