7.4. Withdrawal of individual subjects

Subjects can leave the study at any time for any reason if they wish to do so without any consequences. The investigator can decide to withdraw a subject from the study for urgent medical reasons. Patients leaving the study will receive treatment as deemed appropriate by their treating physician

After randomization, the following patients will leave the interventional part of the study, but clinical data will continue to be collected:

- 1. Patients in whom none of the mycological criteria as described in appendix 1 have become positive within 8 days after randomization. This may be as soon as 48hrs after (e.g. if serum and BAL galactomannan testing and fungal culture result is final 48hrs after randomization).
- 2. Patients in the Netherlands in whom the resistance tests were unsuccessful (asper-gillus culture remained negative and aspergillus PCR demonstrated the presence of A. fumigatus but the resistance PCR is unsuccessful) will receive further treatment according to the choice of the treating physician because guidelines recommend to treat these patients with an azole in combination with a second antifungal drug. If the patient was randomized to the anidulafungin arm, the option will be given to

continue anidulafungin for up to 4 weeks, but these patients will be excluded from the MITT population (see 7.1.4) The 24-week outcome of these patients will be registered. In Belgium, currently no guidelines are in place recommending combination therapy for this patient group. Therefore, this does not apply to Belgian patients. Please note that patients in whom the Aspergenius PCR documents the presence of an aspergillus spp. other than fumigatus will remain in the study and will be included in the MITT population. This specific conclusion will be drawn when the aspergillus spp. PCR is positive with a CT value of 35 or lower but the aspergillus fumigatus PCR is negative as this demonstrates the presence of a non-fumigatus aspergillus infection.

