9. STATISTICAL ANALYSIS

9.1. Primary endpoint analysis

The primary endpoint is defined as all-cause mortality at 42 days (6 weeks) after randomization. The MITT population is considered the main analysis population.

The relation between randomly allocated treatment and the incidence of the primary endpoint in the MITT population will be described by

- the total number of endpoint events by allocated treatment;
 - a crude, unadjusted odds ratio. Logistic regression analysis will be conducted, with randomly allocated treatment as independent predictor variable and the incidence of the primary endpoint as dependent outcome variable;
 - an adjusted odds ratio. A multivariable logistic regression analysis will be applied. The effect of randomly allocated treatment will be adjusted for age, pulmonary or (also) extrapulmonary disease, ICU admission, baseline serum galactomannan status, post allogeneic stem cell transplantation status, and acute or chronic GVHD for which patients are receiving systemic immunosuppressive therapy.

The adjusted odds ratio will be considered the key primary endpoint analysis

The same analysis will be performed for secondary endpoints 2 to 6. The listed sub-populations will be analyzed using simple and multivariable logistic regression (the adjustment factors - as far as applicable - are listed above). Since these analyses will be considered exploratory only and these endpoints are defined as secondary endpoints, no correction for multiple testing will be performed.

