9.3. Multiplicity

There is only 1 primary endpoint and no interim analysis for efficacy will be performed. Therefore, the primary endpoint will be tested at the α =0.05 level (two-sided test).

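### The MITT set that carries the primary analysis is defined inconsistently across sections 5.1, 7.1.2, 7.1.4 and 7.4, above all for Belgian patients with an inconclusive resistance test

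*Protocol*

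**What the plan says.** Section 9.1 states: "The MITT population is considered the main analysis population". The sample size in 9.5 (237 evaluable patients per group, 474 in all) and the futility look in 7.7 (at 237 evaluable patients) are counted in the same set.

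Section 7.1.4 admits randomised patients whose positive mycology was available at randomisation or within 8 days after it, "unless resistance to voriconazole was documented by culture or PCR". It adds that "Dutch patients in whom the resistance PCR or culture turns out unsuccessful will be excluded from the MITT population as well". The reason given is Dutch guidance for cases in which resistance cannot be ruled out.

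Section 7.4 describes the Dutch group more narrowly, as those in whom "culture remained negative and aspergillus PCR demonstrated the presence of A. fumigatus but the resistance PCR is unsuccessful". It puts them outside the MITT and says that this does not apply in Belgium.

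Section 5.1, while explaining treatment duration, mentions patients with demonstrated resistance or an inconclusive test. It names no country and continues: "These patients are not included in the MITT primary endpoint population".

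Three further places bear on the set:
- Secondary endpoints 7 and 8 (7.1.2) concern patients with resistance found during follow-up and label them as MITT.
- The mycology limit is 7 days in 4.2 (criterion 7) and 7.1.3, but 8 days in 7.1.4 and 7.4.
- The primary objective is to "Evaluate if the survival in patients with a triazole susceptible IA can be improved"; section 1 narrows this to documented susceptibility.

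**The concern.** A primary analysis set should sort every randomised patient the same way whichever page is open. Here a Belgian patient with an inconclusive test is in or out depending on the section, and one type of Dutch patient is excluded by one section and not mentioned by the other. This is not detail left to an SAP: the protocol states the rules, and they disagree.

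At stake are who is counted in the primary odds ratio, when 474 and 237 have been reached, and which patients the conclusion describes. If the choice between the rules is made after open-label data have accrued, it becomes a data-dependent choice of the primary population.

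A secondary matter is timing. Section 7.1.4 fixes when a mycology result must be available, not when the sample was taken, and it sets no limit at all for the resistance result that removes a patient. In an open-label trial, a sample taken after allocation is known could therefore decide membership.

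**Working it through.** **The plan's own figure.** Inputs: mortality 35% and 23.33%, power 80% (9.5), two-sided alpha 0.05 (9.3). With pooled variance and no continuity correction:

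n = [1.96·√(2·0.29165·0.70835) + 0.8416·√(0.35·0.65 + 0.2333·0.7667)]² / (0.35 − 0.2333)² = (1.2598 + 0.5365)² / 0.01362 ≈ 237 per group.

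This reproduces 237 (power 0.800). The sample-size arithmetic is not in question; what counts as evaluable is.

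**The rules side by side, for mycology-positive patients.**

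| Patient | 5.1 | 7.1.4 | 7.4 |
|---|---|---|---|
| Belgian, test inconclusive | out | in | in |
| Dutch, culture negative, A. fumigatus PCR positive, resistance PCR failed | out | out | out |
| Dutch, culture negative, Aspergillus PCR negative | out, if this counts as inconclusive | out | not covered |
| Dutch, culture negative, resistance PCR successful, no resistance | in | out as worded; in by its stated reason | in |
| Resistance documented, either country | out | out | not addressed |

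Endpoints 7 and 8 contradict the last row, because they place these patients in the MITT.

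**Size of the Belgian conflict.** Input from section 1: "resistance testing will not lead to an interpretable result in approximately 35% of the patients with IA". Assumed: this share applies in both countries, and the Dutch share d is 0.4 to 0.8. Resistant cases are ignored at first.
- Dutch-only rule: N = 474 / (1 − 0.35·d). For d = 0.4, 474/0.86 = 551; for d = 0.8, 474/0.72 = 658.
- Section 5.1: N = 474 / (1 − 0.35) = 474/0.65 ≈ 730.

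Read strictly, 7.4 excludes fewer Dutch patients than this, so 551-658 is an upper limit for that section.

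Now remove resistant cases among patients with a result, using section 1's 15% for the Netherlands and 5% or 13% for Belgium. The share kept under the Dutch-only rule is d·0.65·0.85 + (1−d)·[0.35 + 0.65·(1−r)], where r is the Belgian prevalence. Under 5.1 the 0.35 term drops out. Over the same range of d, N is about 591-758 under the Dutch-only rule and 801-854 under 5.1.

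If enrolment were instead fixed so that the Dutch-only rule gave 474, section 5.1 would leave about 345-422 patients, with power of about 67-75%. The protocol states no randomised total, so this is only a conditional illustration.

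**Size of the timing point, all inputs assumed.** Suppose no true effect and 35% mortality. Let 5-15% of potential members qualify only through a late sample, with mortality 50-60%, and let all of them be found in one arm but 50-80% in the other. The spurious difference is 0.2 to 2.0 points and the type I error 5.0-7.5%. Its sign depends on which arm is sampled more.

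For late-found resistance, suppose 3% of controls and 1% of combination patients are removed, with mortality 70% (within the 50-88% in section 1). Control mortality becomes (0.35 − 0.021)/0.97 = 33.9% and combination (0.35 − 0.007)/0.99 = 34.6%, about 0.7 points against combination. The planned difference is 35 − 23.33 = 11.67 points.

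**The case against.** The best defence is that 7.1.4 is the definitions section, 7.4 refers back to it, and 5.1 is an aside about duration. Keeping Belgian patients is deliberate and explained. That shows which rule was probably meant. It does not remove the contrary statement in 5.1, which names the primary endpoint population explicitly.

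Several stronger readings are tempting, but the documents do not support them.
- A reader might infer from the word "or" in 7.1.4 that every culture-negative Dutch patient is dropped. If half the patients were Dutch and half of those culture negative, this would raise the need to 474/0.75 = 632. The same sentence's reason (resistance cannot be excluded) and exclusion criterion 6 (negative sputum cultures and no BAL) both suggest that either test suffices. The wording is loose, but this reading is unlikely.
- A reader might take the day 3, 5 and 7 sera as admitting patients. Appendix 2 describes their sampling and storage; it does not say that they are tested in real time. For most patients, 4.2 requires mycology at inclusion; only the subset under criterion 7 may await it.
- The objective's wording is a mismatch with the population, not another MITT rule.
- Non-fumigatus cases are not left open: 7.4 places them in the MITT.
- The absence of an ITT analysis from section 9 is not a defect in itself, since the SAP is not shown and may contain one.

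Two cautions on size stand. Criterion 6 keeps out Dutch patients who cannot be tested, so 35% may be too high for those enrolled. Figure 1, to which 7.1.4 refers, is not shown and may settle some cases.

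**Conclusion.** Wrong as written. The protocol contradicts itself on the primary analysis set in three ways: Belgian patients with an inconclusive test (5.1 against 7.1.4 and 7.4), Dutch patients negative on both culture and Aspergillus PCR (7.1.4 against 7.4), and resistant patients (7.1.4 against endpoints 7 and 8). The 7- and 8-day limits and the objective's wording are lesser inconsistencies.

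On the stated assumptions, the first conflict is worth roughly 70 to 180 mycology-positive patients (730 less 658 or 551) for the same 474 evaluable. The national split is not in the protocol, and the 35% is a general figure for invasive aspergillosis. A reader might go on to conclude that the primary result would change with the rule. What is shown is a change in membership and in the enrolment needed; neither the direction nor the size of any change in the odds ratio can be derived.

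The sampling-time gap is real but secondary: the likely bias is modest and its direction unknown.

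**What to change.** Put one operational definition in 7.1.4 and align 4.2, 5.1, 7.1.2, 7.1.3, 7.4 and Figure 1 to it, before any outcome data by arm are seen. It should:
- state one rule for Belgian patients without a resistance result;
- write the Dutch rule unambiguously, for example as neither culture nor PCR giving an interpretable result, or otherwise if that is not what is meant;
- place Dutch patients negative on both culture and Aspergillus PCR explicitly, and carry over the existing rule for non-fumigatus cases;
- use one day limit for mycology;
- base mycology and resistance status on samples taken by a fixed time point chosen by the sponsor and applied identically in both arms, whenever the result arrives.

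Move endpoints 7 and 8 to the ITT population. If Belgian patients without a result stay in, reword the objective to disease not documented as triazole resistant. Add a 42-day mortality sensitivity analysis in all randomised patients, if the SAP does not already have one; survival is already collected for patients who leave (7.4, 7.6, 12.1).

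How patients without a resistance result are treated is left to the sponsor; only the statements about them must be reconciled.

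The cost is an amendment to wording and at most one further analysis, with no new data. The sampling window has a small downside: a few patients whose only positive sample is late would leave the MITT.
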